6.4 Sample Size

The sample size in Stage 1 is based on the 3 + 3 design. In Stage 2, no formal sample size calculation was performed. The number of patients planned to recruit is guided by practical rather than statistical considerations.

Stage 1 (dose-escalation) will enroll approximately 12 patients (range: 6 - 24 patients).

Stage 2 (dose expansion) will enroll 20 at the MTD established in Stage 1 for QD dosing.

The total sample size for this study is approximately 32 patients (range: 26 - 44 patients).

6.5 Recruitment

To achieve adequate patient enrollment to reach the targeted sample size, Kazia Therapeutics Limited and the CRO will adopt a close collaboration with the recruiting Investigators. This will ensure timely discovery and resolution of any recruitment related issues that may be encountered.

7 Monitoring

7.1 Cohort Review Committee

On the basis of the review of real-time safety data and available preliminary PK data from this study with GDC-0084, dose-escalation may be halted or modified by Kazia Therapeutics Limited as deemed appropriate.

Decisions regarding dose-escalation and selection will be made by a CRC including the medical monitor, recruiting Investigators, sponsor representative and any other relevant and necessary expert on as needs basis, according to the CRC charter. For dose-escalation purposes, and selection of appropriate dose levels and schedules DLT assessments and other safety/PK will be reviewed by Kazia Therapeutics Limited in consultation with the Investigators during CRC meetings.

7.2 Interim Analysis and/or Stopping Guidelines

A description of planned analyses is shown in Section 6. There is no interim analysis planned for early efficacy or futility/early stopping. Guidelines for discontinuing the study are given in Section 4.11.

Version: Amendment 4 Date: 31 Mar 2020

Protocol Number: NVGN-0084-201

IND Number: 112.608

7.3 **Clinical Monitoring**

The study will be monitored by a CRO. Its representatives will be allowed access to all information resulting from this study and Kazia Therapeutics Limited will have an unrestricted right to use such information. The study monitor will have access to laboratory test reports and other patient records needed to verify the entries on the CRF. The patients' confidentiality will be respected as required by local law.

The sponsor and the CRO are responsible for ensuring the proper conduct of the study with regards to protocol adherence and validity of the data recorded on the CRFs. Therefore, a clinical monitor is assigned to the study. With duties to aid the Investigator and at the same time, the CRO, in the maintenance of complete, legible, organized and easily retrievable data. In addition, a clinical monitor will explain, interpret and ensure the Investigator's understanding of all applicable regulations concerning the clinical evaluation of the investigational product and ensure an understanding of the protocol, reporting responsibilities and the validity of the data.

Details on data collection and monitoring activities can be found in the study's Monitoring Plan.

7.4 Auditing

This study may be audited by Kazia Therapeutics Limited or its designee to verify the authenticity of recorded data, protocol adherence and compliance with ICH-E6. Patients participating in the study should be informed that their records might be reviewed for this purpose, and by government health authorities. The patients' confidentiality will be respected as required by local law.

Further, audits at a study site may take place at any time during or after the study. The independent audit can be carried out by the CRO's or Kazia Therapeutics Limited's quality assurance personnel (including a third-party auditor contracted by Kazia Therapeutics), or a regulatory authority.

Pharmaceutical Information

Investigational Product

GDC-0084 is a potent, oral, selective, brain-penetrant small molecule inhibitor of class I PI3K and mTOR kinase which has been specifically developed for the treatment of brain cancer.

GDC-0084 Name:

(5-(6,6-dimethyl-4-morpholino-8,9-dihydro-6H-[1,4]oxazino[3,4-e]purin-2-Active ingredient:

yl)pyrimidin-2-amine)

Excipients: Microcrystalline cellulose, lactose monohydrate, croscarmellose sodium, and

colloidal silicon dioxide

Presentation: White conforming opaque size 0 capsules for oral administration manufactured in

accordance with Good Manufacturing Practice (GMP)

15 mg GDC-0084 per capsule Dosage:

Batch numbers and retest/expiry dates will be documented in the TMF and in the final clinical study report.

8.2 Supply, Packaging and Labeling

The 15 mg GDC-0084 capsules will be produced and supplied by Kazia Therapeutics vendor(s) in accordance with GMP.

Primary packaging of the product will be 60CC white high-density polyethylene round bottle, induction sealed with child resistant closure. Each bottle contains 35 capsules.

Version: Amendment 4 Date: 31 Mar 2020

Protocol Number: NVGN-0084-201

IND Number: 112.608

Clinical labeling, warehousing and distribution, including returns, will be organized centrally. The label will contain the information as required by the relevant regulatory authority and national requirements. Labelling will be performed according to GMP and ICH GCP guidelines and local law.

Storage and Handling

The investigational product must be stored in securely locked areas not generally accessible until dispensed to the patients. The medication must be stored at between 15°C and 30°C (59°F-86°F).

The key to the storage area is to be kept by the Investigator or other person responsible for the medication. The store will be accessible only to those persons authorized by the Investigator to dispense study medication. The Investigator is responsible for the dispensing of medication according to the dosage regimen outlined in this protocol. All investigational product (partly used, unused and empty packaging) is to be left in the original packaging and must be returned to Kazia Therapeutics Limited's nominated vendor for destruction at the end of the study.

Accountability

The investigational product supplied by Kazia Therapeutics Limited is to be used exclusively in this clinical study according to the instructions of this protocol.

The Investigator must confirm the receipt of the investigational product with his/her signature. A copy of this receipt must be kept by the Investigator and another copy will be stored in the TMF. It is requested that any damaged or defective investigational product is promptly reported to the CRO and Kazia Therapeutics Limited.

The Investigator, or an approved representative (e.g. pharmacist), should maintain records of the product's delivery to the study site, the inventory at the site, the use by each patient, and will ensure that all investigational product is stored in a secured, limited access area. These records should include dates, quantities, batch/serial numbers, retest/expiration dates (if applicable), and the unique code numbers assigned to the investigational product(s) and study patients. Investigators should maintain records that document adequately that the patients were provided with the doses specified by the protocol and reconcile all investigational product received from Kazia Therapeutics Limited's vendors.

All used and unused supplies must be retained for verification and drug accountability and must be returned to Kazia Therapeutics Limited's nominated vendor for destruction after completion of the study.

To ensure adequate records, all investigational product will be accounted for on an ongoing basis throughout the study in accountability forms at the study site. Records will be kept in accordance with the applicable regulatory requirements and the Investigator will ensure that the investigational product is dispensed only by qualified site staff.

Preparation and Administration

The capsules should never be opened and should be swallowed whole, not chewed.

In Stage 1, patients will be instructed to take the capsules according to the current dose level investigated as a single dose. For Stage 2, doses depend on the findings of Stage 1. Timing of intake in relation to food or beverage consumption and other procedures is outlined in the respective sections on study design (Section 3.7) and assessments (Section 4.64.6).

During the PK sampling period, i.e. from Enrollment/Week 1 until Day 1 of Cycle 2, patients will take GDC-0084 under supervision of qualified study site personnel, at least 15 min after the pre-dose PK blood sample. Thereafter, patients will take their GDC-0084 dose self dependently and compliance will be checked every 4 weeks by the Investigator.

in the Investigator's Brochure (IB).

Version: Amendment 4 Date: 31 Mar 2020

8.6 Warnings and Precautions

Information on known AEs and potential risks associated with the investigational product as well as further guidance for the Investigator on safety monitoring and management for specific can be found

Protocol Number: NVGN-0084-201

IND Number: 112.608

8.7 Prior and Concomitant Medication

8.7.1 Prior Medication

Medications not permitted before the start of the study (i.e., before first intake of the study drug) are:

 Previous radiotherapy to the brain or cytotoxic drug therapy (including Gliadel wafers) in addition to the required postoperative radiation plus TMZ, non-cytotoxic drug therapy.

8.7.2 Concomitant Medication

Medications not permitted at any point during the course of this study are:

- Insulin therapy;
- Strong CYP3A4 inducing or inhibiting agents;
- Other investigational drugs.

9 Correlative Studies

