Version: Amendment 4 Date: 31 Mar 2020 Protocol Number: NVGN-0084-201

IND Number: 112,608

A phase 1 open-label, dose-escalation study (Wen et al, J Clin Oncol 34, 2016; NCT01547546), has been completed in 47 patients with progressive or recurrent high-grade gliomas. GDC-0084 was given once daily in cycles of 28 days. This first-in-human, phase 1 dose-escalation study of GDC-0084 at doses between 2 and 65 mg once daily demonstrated a safety profile consistent with classic PI3K/mTOR-inhibitor related adverse events (AEs) with the most frequent AEs attributed to GDC-0084 being fatigue, hyperglycemia, nausea, rash, hypertriglyceridemia, mucositis, hypophosphatemia, decreased appetite, and diarrhea with the most common Grade 3 AEs related to GDC-0084 being hyperglycemia (8.5%) and mucositis (6.4%). Dose limiting toxicities (DLTs) included 1 case of Grade 2 bradycardia and Grade 3 myocardial ischemia (15 mg), Grade 3 stomatitis (45 mg), and 2 cases of Grade 3 mucosal inflammation (65 mg).

The dose proposed for the current study is based on the results of the previous phase 1 study (Wen et al, J Clin Oncol 34, 2016; NCT01547546), which defined the maximum tolerated daily dose (MTD) of GDC-0084 in patients with high grade gliomas (WHO Grade III–IV), who had progressed during or after treatment with at least 1 prior XRT-containing regimen for gliomas and/or were not candidates for regimens known to provide clinical benefit. The MTD was determined to be 45 mg when GDC-0084 was administered orally once daily (QD) in cycles of 28 days in these patients.

However, for newly diagnosed GBM patients a dose of 60 mg may be more suitable. A higher clinical exposure is expected to be more effective, but still tolerable, in this healthier patient group,

Thus, the starting dose in this Phase 2a study is 60 mg given orally QD in 28-day cycles.

PK analysis in the phase 1 study confirmed GDC-0084 was rapidly absorbed and demonstrated linear and dose-proportional increases in exposure, with an elimination half-life supportive of both once daily and intermittent dosing. In this population of patients, the AEs and other safety findings were generally consistent with the established PI3K/mTOR inhibitor class effects and/or with the disease under study. The MTD was determined to be 45 mg in this patient population. The data therefore warrant further development of GDC-0084 in phase 2 studies in patients with newly diagnosed GBM with unmethylated O₆-MGMT promoter status.

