4.2.2 Exclusion Criteria

Patients presenting with any of the following will not be included in the study:

- 1) Previous radiotherapy to the brain or cytotoxic drug therapy (including Gliadel® wafers) in addition to the required postoperative radiation plus TMZ, non-cytotoxic drug therapy, or experimental drug therapy directed against the brain tumor prior to this regimen, will be excluded. Patients may have received or be receiving corticosteroids, analgesics, and other drugs to treat symptoms or prevent complications but the dose must be stable at treatment start. NOTE: 5 aminolevulinic acid-mediated photodynamic therapy administered prior to surgery to aid in optimal surgical resection is not considered a chemotherapy agent;
- 2) Any prior, or anticipated, concomitant treatment involving a medical device (such as Optune®) applying tumor treating fields (TTF). Prior short-course Optune® monotherapy (i.e. without concurrent TMZ or other chemoRx) may be allowed with approval from the Medical Monitor
- 3) QT interval time of ≥ 470 msec;
- 4) Undetermined/indeterminate MGMT status;
- 5) Diabetic patients and/or ongoing use of insulin therapy; clinically confirmed prediabetic patients;
- Use of any strong CYP3A4 inducing or inhibiting agents within 14 days of first dose of GDC-0084;
- 7) Significant medical illnesses that in the Investigator's opinion cannot be adequately controlled or would compromise the patient's ability to tolerate this therapy;
- 8) Women who are pregnant (determined by serum beta chorion-gonadotropin) or who are lactating. NOTE: Serum pregnancy test to be assessed within 7 days prior to first dose;
- 9) Any disease likely to obscure toxicity;
- 10) Diagnosed with infratentorial GBM;
- 11) Diagnosed with tumor outside of brain;
- 12) Diagnosed with gliomatosis cerebri;
- 13) Evidence of recent hemorrhage on postoperative MRI of the brain. However, patients with clinically asymptomatic presence of hemosiderin, resolving hemorrhagic changes related to surgery, and presence of punctate hemorrhage in the tumor are permitted entry into the study;
- 14) Male and female patients of childbearing potential unwilling or unable to use effective means of contraception (oral contraceptives, intrauterine contraceptive device, barrier method of contraception in conjunction with spermicidal jelly) throughout the study and for at least 28 days after the last dose of assigned treatment;

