Prior to the scheduled FDG injection, patients should fast for at least 4 hours (preferably 6 hours). The blood glucose level should be determined at the time of the FDG-PET scan. Use of anti-hyperglycemic medications, including insulin, immediately prior to the FDG-PET scan is not permitted, as these agents will impact FDG uptake and compromise the interpretability of the FDG-PET scan. Specifically, no short-acting insulin should be administered within 4 hours prior to FDG administration.

Median and mean FDG-PET standard uptake value within the contrast enhancing, measurable target lesion(s), contralateral normal-appearing cortical tissue, and contralateral normal-appearing white matter will be quantified.

4.6.4 **Cardiac Assessment**

Cardiac assessment will be performed by the Investigator and be based on assessment of medical history, physical examination, 12-lead ECG results (including QTc) and evaluation of LVEF by echocardiography (ECHO) or multi-gated scan (MUGA) as well as, as clinically indicated, measurement of troponin T and B-type natriuretic peptide as potential biomarkers of early

Version: Amendment 4 Date: 31 Mar 2020

cardiotoxicity. Cardiology consult may be sought by the Investigator if required to confirm suitability for inclusion in the study.

Protocol Number: NVGN-0084-201

IND Number: 112.608

Except for baseline ECGs at screening, ECGs should be conducted approximately 2 hours post-dose, to coincide with the approximate timing of T_{max} determined in a prior clinical study.

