4.10 Supportive Care Guidelines

Participants will follow their oncology care plan. All medications required as part of a participant's normal clinical care for support of their medical conditions are permitted during the study, except for prohibited medications listed below. All concomitant medications must be recorded in the source documentation and in the CRFs for the duration of patient participation.

The following medications/treatments are prohibited during the study:

- Another investigational drug;
- Strong Cytochrome P450 subtype 3A4 (CYP3A4) inhibitors (such as but not limited to, atazanavir, clarithromycin, indinavir, itraconazole, ketoconazole, nefazodone, nelfinavir, ritonavir, saquinavir, telithromycin, troleandomycin, voriconazole, and grapefruit juice) or strong CYP3A4 inducers (such as but not limited to, rifampin, carbamazepine. rifapentine, phenytoin, phenobarbital, and St. John's wort or hyperforin).

Version: Amendment 4 Date: 31 Mar 2020

Protocol Number: NVGN-0084-201

IND Number: 112,608

Enzyme-inducing anti-epileptic drugs should also be avoided. If use of such drugs is necessary, the risks and benefits should be discussed with the medical monitor prior to its concomitant use with GDC-0084.

Based on nonclinical toxicology findings for GDC-0084, known toxicities associated with PI3K and mTOR inhibitors (including rapamycin analogues) in the clinic, and clinical safety data from study G028070, the guidelines for monitoring and management of specific toxicities detailed below should be considered.

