4.10.1 Hyperglycemia and Metabolic Effects

It is known that PI3K-mTOR pathway inhibitors can affect glucose and/or insulin metabolism, leading to hyperglycemia. Cases of hyperglycemia, including Grade 3 in severity, have been observed in the GDC-0084 single-agent study GO28070. Glucose levels at baseline and during study should be carefully monitored, and appropriate dose delays/dose modifications for managing hyperglycemia should be implemented per protocol quidelines. Patients should be instructed to report symptoms associated with hyperglycemia such as thirst, frequent urination, and blurred vision. Use of oral anti-hyperglycemic agents, such as metformin, for patients experiencing Grade ≥ 2 hyperglycemia may be implemented. Anti-hyperglycemic agents should be used to control severe hyperglycemia per institutional standard of care.

Other metabolic effects known to be associated with mTOR inhibitors include hyperlipidemia. Cases of low-grade hypercholesterolemia and hypertriglyceridemia have been observed in the GDC-0084 single-agent study GO28070. Cholesterol and triglyceride levels should be monitored per protocol guidelines. Use of lipid-lowering therapy for patients experiencing Grade ≥ 2 elevations may be initiated per institutional standard of care and protocol guidelines.

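### Section 8.7.2 bans insulin throughout the study, but Section 4.10 omits it from its prohibited list, so sites have conflicting instructions for severe hyperglycemia that arises on treatment.

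*Combined protocol and SAP*

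**What the plan says.** Section 8.7.2 lists what is forbidden: "Medications not permitted at any point during the course of this study are". The first of its three items is "Insulin therapy". The others are strong CYP3A4 inducers or inhibitors and other investigational drugs. No exception is given for rescue or emergency use.

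Section 4.10 states a general permission. Medications that are part of a participant's "normal clinical care for support of their medical conditions are permitted during the study, except for prohibited medications listed below". The list that follows has two items: another investigational drug, and strong CYP3A4 inhibitors or inducers. A caution to avoid enzyme-inducing anti-epileptics comes after it. Insulin does not appear.

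Section 4.10.1 covers management of hyperglycemia. It allows oral agents, with metformin as the example, from Grade 2 upward, and refers to dose delays and modifications. For severe cases it says: "Anti-hyperglycemic agents should be used to control severe hyperglycemia per institutional standard of care".

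Section 4.6.3 deals with insulin in the imaging context: "Use of anti-hyperglycemic medications, including insulin, immediately prior to the FDG-PET scan is not permitted", and more specifically "no short-acting insulin should be administered within 4 hours prior to FDG administration".

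Exclusion criterion 5 in Section 4.2.2 bars entry to "Diabetic patients and/or ongoing use of insulin therapy; clinically confirmed prediabetic patients".

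**The concern.** Exclusion 5 settles insulin use at entry. It leaves open whether insulin may be started on study for hyperglycemia caused by the drug.

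Hyperglycemia is a known effect of this drug class and was the most common related Grade 3 event in phase 1 (Risk/Benefit Analysis). The dose-limiting toxicity definition in Section 3.7.1 itself foresees symptomatic cases with dehydration or acidosis that need hospital care. A clinician reading Section 4.10 would conclude that insulin may be given. One reading Section 8.7.2 would conclude that it may not.

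The reading also affects the patient's status in the study. Section 4.11.1 names administration of an excluded medication as a reason for withdrawal by the investigator. Section 6.3.1 bases the per-protocol subset partly on major deviations, with criteria still to be fixed before database lock. The same clinical act could therefore be routine care at one site and a deviation at another.

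**Working it through.** The plan gives no figure to reproduce on this point. The check has two parts: a comparison of the text, and a rough count of how often the situation could arise.

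**Text comparison: may insulin be started on study?**

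| Section | Rule on insulin | Answer |
|---|---|---|
| 4.2.2, exclusion 5 | Bars diabetes, prediabetes and ongoing insulin at entry | Not addressed |
| 4.6.3 | Treats insulin as an anti-hyperglycemic medication; restricts it only just before FDG-PET, with a 4-hour limit for short-acting insulin | Implies yes, outside that window |
| 4.10 | Normal-care medication allowed except its own list; insulin not on the list | Yes |
| 4.10.1 | Anti-hyperglycemic agents for severe cases, following institutional practice | Not excluded |
| 8.7.2 | Forbidden throughout the study | No |

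Three points follow.

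1. The exception in 4.10 is tied to the list printed beneath it, so 4.10 does not import the ban in 8.7.2. Two of the three items in 8.7.2 are repeated in 4.10. Insulin is the only one missing.
2. Section 4.10.1 specifies oral agents for Grade 2 and above but drops that qualifier for severe hyperglycemia. With 4.6.3 counting insulin among the anti-hyperglycemic medications, the natural reading of 4.10.1 includes insulin.
3. A 4-hour limit on short-acting insulin has no function if insulin is never allowed.

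**How often could it arise?**

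Inputs: 47 phase 1 patients and an 8.5% rate of related Grade 3 hyperglycemia (Risk/Benefit Analysis); planned total of about 32, range 26 to 44 (Section 6.4). The count of 4 is inferred, because 4/47 = 8.5%.

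- Clopper-Pearson 95% interval for 4/47: 2.37% to 20.38%.
- N = 32: 32 × 4/47 = 2.72 patients; over the interval, 32 × 0.0237 = 0.76 to 32 × 0.2038 = 6.52.
- N = 26: 26 × 4/47 = 2.21.
- N = 44: 44 × 4/47 = 3.74.

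This assumes that the phase 1 rate carries over. Phase 1 used 2 to 65 mg in progressive or recurrent glioma. This trial starts at 60 mg, which could raise the rate, and excludes diabetic and prediabetic patients, which could lower it.

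**The case against.** The best reply is that the sections do not strictly collide. Section 4.10 permits normal-care medication but does not require insulin. A site that never gives insulin breaches neither section, and 4.10.1 can be followed with metformin, other non-insulin agents and dose holds. On this view the specific ban narrows the general permission, and the defect is only an incomplete duplicate list. That is formally right. But nothing in the protocol says that only non-insulin agents may be used, or what to do when they fail. Compliance with both sections is then achieved by withholding insulin in the cases where it may be needed most.

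A second reply is that a patient with acidosis would have a dose-limiting toxicity and leave treatment (Sections 3.7.1, 4.7 and 4.11.2). This narrows the problem but does not remove it. The criterion covers only symptomatic fasting events of Grade 3 or worse in Cycle 1. Sections 3.7.1 and 4.9.2 let patients continue after a reversible toxicity if the investigator and medical monitor agree. The ban also runs for the course of the study, and patients stay in follow-up after treatment stops.

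Third, the practical stakes are limited. Withdrawal under 4.11.1 is discretionary, and Section 10.4 allows deviations to remove an immediate hazard. The phase 1 dose-limiting toxicities named in the protocol do not include hyperglycemia, although that list may not be complete and the phase 1 definition is not shown. Section 8.6 refers sites to the Investigator's Brochure, whose content on this point is unknown. All of this stands and limits the severity. None of it makes the sections agree.

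Finally, the documents do not show whether the ban was deliberate. That bears on which remedy to choose, not on whether one is needed.

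**Conclusion.** The concern holds. Section 8.7.2 forbids insulin without exception, Section 4.10 permits it by omission, and Section 4.6.3 is written as though it may be used. Followed literally, 8.7.2 would deny insulin for a foreseeable toxicity of the study drug.

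On the carry-over assumption, about 2.7 of 32 patients would have a related Grade 3 hyperglycemia event, with 0.8 to 6.5 consistent with the phase 1 data. Over the planned sample-size range, the point estimate runs from 2.2 to 3.7. The number in whom the conflict would matter, those who fail non-insulin agents and dose holds, cannot be estimated from the documents and can be no larger than the number with severe hyperglycemia.

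No sample size, dose-escalation rule or primary endpoint depends on this. It is a safety instruction that should be corrected, and patients are not left without recourse in the meantime.

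**What to change.** Use a single prohibited-medication list, the same in Sections 4.10 and 8.7.2, and keep exclusion 5 as it stands. Amend 8.7.2 to permit short-term rescue insulin for hyperglycemia of Grade 3 or worse, managed under 4.10.1 and outside the 4-hour pre-FDG window in 4.6.3. State that such use is not an excluded medication for the purposes of 4.11.1.

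If the sponsor does intend a total ban, add insulin to the list in 4.10. State in 4.10.1 that only non-insulin agents and dose holds may be used, and say what happens to a patient in whom these fail.

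The cost is a change of protocol wording. Rescue insulin would be recorded as a concomitant medication, which 4.10 already requires for all such medications.
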